## 9. STATISTICAL CONSIDERATIONS

### 9.1 General Design Issues

In this randomized, controlled, double-blinded clinical trial, eligible children will receive in a 1:1:1 ratio either 600 IU or 1000 IU or 2000 IU vitamin D3 supplementation orally once daily for six months. Our primary outcome measure will be brachial FMD at 6-month follow-up. A 25% or more improvement in brachial FMD% in the 1000 IU or the 2000 IU group when compared to the 600 IU group, after six months of vitamin D replacement will be considered significant.

Our secondary outcomes will include: (1) pulse wave velocity (PWV) as a measure of arterial stiffness, (2) 1/fasting insulin concentration as a surrogate for insulin sensitivity, and (3) metabolic syndrome risk factors (blood pressure, waist circumference, HDL cholesterol, triglycerides, and fasting blood glucose) at the 6-month follow-up.

### 9.2 Sample Size and Randomization

Our sample size estimates are based on showing a relative improvement in baseline brachial artery flow mediated vasodilation (FMD, %) of at least 25% in children receiving each of the higher doses of vitamin D3 (1000 IU and 2000 IU) compared with no improvement in the 600 IU group after six months of treatment. We assumed the baseline FMD was ~6.5% based on previous studies in overweight children similar to our projected population. A sample size of 56 in each treatment group at the end of the trial would have 84% power (two-sided two-sample comparison of means,  $\alpha=0.025$ ) to detect this clinically important difference of 25% relative improvement (absolute improvement=25%\*6.5%≈1.6%) assuming a standard deviation of 2.6% (conservative estimates based on published literature). To provide for a projected drop-out rate of 25% by the end of the trial, we propose to recruit 225 children into the trial. We have over 90% power to detect a dose-response effect by testing for linear trend assuming a 0%, 20%, and 30% improvement in vascular health among children receiving 600 IU, 1000 IU, and 2000 IU, respectively.

Our original sample size of n=252 was based on 90% power and 20% attrition to allow for subgroup analyses by race. In December of 2015, the PI and funder decided to re-evaluate the targeted sample size due to slower than expected recruitment. Accordingly, with approval from NHLBI, our accrual target was revised from 252 participants to 229 participants based on projected enrollment and power of at least 80% to detect the original effect size with 25%-30% attrition. The lower sample size of n=225 would still allow for detection of clinically significant effect of vitamin D supplementation. However, the proportion of African Americans in the recruited sample was much larger than anticipated; the small number of Caucasian subjects in the cohort precludes doing race-stratified analysis. For the secondary outcomes, we have 89% power to detect effect sizes of 0.61 or greater without adjustment for multiplicity.

### Treatment Assignment Procedures

In this randomized, controlled, double-blinded clinical trial, eligible children will be randomly allocated, using a permuted block design, in 1:1:1 ratio, to receive either conventional (600 IU)

or enhanced (1000 IU or 2000 IU) vitamin D3 supplementation orally once daily for six months. Study supplement bottles were masked and labeled by the research pharmacist with appropriate randomization codes. At enrollment, the CRHC database assigned the randomization code based on the permuted block scheme.

Study participants or investigators will not have access to the assigned doses until the end of the clinical trial [timing of planned breaking of randomization code]. Unmasking may occur in the instance of an SAE. The ISM may divulge the masked dosage to the PI or relevant clinicians who are treating the patient.

### **9.3 Interim analyses and Data and Safety Monitoring Plan**

No interim efficacy analysis has been planned. [name] will work with [name] to prepare a DSMB report addressing specific concerns that she anticipates the DSMB may have regarding the conduct of the study. This will be distributed to DSMB members along with the Open Session report. Likewise, [name] report for the Closed Session will usually contain an assessment of the progress of the trial, including recommendations as to whether it should be terminated or modified. Interim data reports will generally include the following types of information, although only the Closed Session data reports will include comparisons by treatment group:

- Monthly and cumulative accrual compared with targets
- Baseline characteristics, overall and by treatment group
- Completeness and quality of data collection forms
- Status of enrolled participants, overall and by treatment group
- Participants' off-protocol treatments
- Compliance with eligibility criteria and other protocol requirements
- Subject adherence to the treatment regimen, overall and by treatment group
- Individual SAEs by subject ID number and a table of event-specific cumulative rates, overall and by treatment group

[name] will work to ensure that all the information presented at the DSMB meetings remains confidential. Each report will be marked as such. At the end of each DSMB meeting, all reports will be collected and destroyed. At the end of the meeting, the DSMB will make recommendations regarding the continuation of the trial. [name] will implement the DSMB recommendations. [name] will also submit the DSMB recommendations to the IRB.

### **9.4 Outcomes**

#### **Primary outcome**

Our primary outcome measure will be change in mean FMD% at 6-month follow-up. A 25% or more improvement in FMD% in the 1000 IU or 2000 IU compared to the 600 IU group after six months of vitamin D replacement will be considered significant.

#### **Secondary outcome**

Our secondary outcomes will include: (1) pulse wave velocity (PWV) as a measure of arterial stiffness, (2) 1/ fasting insulin concentration as a surrogate for insulin sensitivity, and (3) metabolic syndrome risk factors (blood pressure, waist circumference, HDL cholesterol, triglycerides, and fasting blood glucose) at the 6-month follow-up.

## 9.5 Data Analyses

Our primary analysis will use children's original treatment assignment regardless of adherence (intention to treat). We will begin by calculating descriptive statistics for baseline demographics and clinical characteristics by vitamin D treatment groups (600 IU vs 1000 IU vs 2000 IU). Our primary outcome measure of vascular health is brachial artery FMD expressed as a percentage. We will use mixed-effects models with fixed effects of time (baseline, 3 months, and 6 months), the treatment\*time interaction, and random subject effects to test for differential changes in FMD over time and differences in FMD at six months. We are primarily interested in the comparisons of each higher dose (1000 IU and 2000 IU) to the lower dose (600 IU) at six months ( $\alpha=0.025$  for each comparisons). The mixed-effects model will allow unbiased estimation of the treatment effects at six months even if some 6-month data are missing because of the incorporated dependence among baseline, 3-month and 6-month assessments (assuming data are missing at random). We will test the main effect of vitamin D supplementation (three groups) at 3 and 6 months and pairwise comparisons of the groups receiving the larger doses of vitamin D with the group receiving 600 IU. If differences are detected across the 3 groups, we will test for a dose response in FMD across doses by using a linear contrast of coefficients test ( $\alpha=0.05$ ). We will use the same methodology to test the effects of higher doses of vitamin D on pulse-wave velocity, our primary measure of arterial stiffness.

The second part of our primary analysis of our trial is to determine whether higher doses of vitamin D will result in improvements in insulin sensitivity and metabolic syndrome markers over time. We will use mixed-effects models with fixed effects of time (baseline, 3 months, and 6 months), and the treatment time interaction with random subject effects to test for differential changes in secondary outcomes over time. We will test the main effect of treatment (three groups) at 3 and 6 months and pairwise comparisons of the groups receiving the larger doses of vitamin D with the group receiving 600 IU. All tests will be two sided with  $\alpha=0.05$ .

We will explore the mediating effects of inflammatory markers (hs-CRP, IL-6, TNF- $\alpha$ ) and adipokines (leptin and adiponectin) on the temporal relationship between vitamin D and vascular health. We hypothesize that vitamin D effects on vascular health may be driven by inflammatory processes and adipokines. An analysis that would complement this hypothesis would be a mediation analysis where we demonstrate that the effect of vitamin D on vascular health is partially mediated by our measures of inflammation and adipokines. We propose to use single-mediator and multiple-mediator methods incorporating product of coefficients to test for mediation. For the simple single-mediator analysis, we first must demonstrate that the high dose vitamin D has a significant effect on each mediator (inflammatory markers and adipokines) at three and six months using a general linear model. We will then test whether 6-month vascular health is correlated with each mediator. Both tests would have to be significant for there to be evidence of mediation. We will estimate the mediated effect by taking the product of the following coefficients: 1) the coefficient for the intervention effect on the mediator, and 2) the coefficient for the mediator in a model testing the intervention effect on

vascular health controlling for the potential mediator. This estimate will provide the reduction in the effect of vitamin D on vascular health when adjusted for the mediator. The confidence interval for the mediated effect will be calculated using bootstrap methods. Since our vitamin D intervention is hypothesized to target multiple mechanisms, we will test for a multiple-mediator model after single mediation is thoroughly investigated.

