**Design and Outcomes**

In a double-blinded, controlled trial, we propose to randomize 229 eligible children to receive either 600 IU (conventional supplementation, current recommended dietary allowance), or 1000 IU or 2000 IU (enhanced supplementation) of vitamin D3 daily for six months.

The primary outcome measure will be change in brachial flow-mediated dilation percentage at 6 months (FMD%); FMD% is a measure of vascular endothelial function. The secondary outcome measures will include (1) pulse-wave velocity (PWV) – a measure of arterial stiffness, (2) central and systemic blood pressure, (3) fasting blood glucose concentration, (4) 1/fasting insulin concentration as a surrogate for insulin resistivity, (5) lipid profile indices, (6) adipocytokines (plasma leptin, and adiponectin) and systemic markers of inflammation (plasma high-sensitivity CRP, IL-6, TNF- $\alpha$ ).

Eligible participants will be scheduled for enrollment within eight weeks of the initial screening visit. Follow-up visits will occur approximately at three months and six months after enrollment. FMD%, PWV, biochemical measurements, and inflammatory markers will be obtained at each study visit; DXA scan will be done at enrollment and at 6 months.

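### The primary outcome is defined both as change in FMD% and as the 6-month value, and the analysis section does not say which contrast decides the trial

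*Combined protocol and SAP*

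**What the plan says.** **Outcome definitions.** The synopsis (Design and Outcomes) makes the primary outcome the change in brachial FMD% at 6 months. Section 9.4 agrees: "Our primary outcome measure will be change in mean FMD% at 6-month follow-up". Section 9.1 differs: "Our primary outcome measure will be brachial FMD at 6-month follow-up".

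**Analysis.** Section 9.5 specifies intention to treat, 1000 IU and 2000 IU each against 600 IU, six months, and alpha 0.025 for each comparison. The model has fixed effects of time (three visits) and treatment by time, "and random subject effects to test for differential changes in FMD over time and differences in FMD at six months". No treatment main effect, baseline covariate or constraint on baseline means is mentioned. The section adds: "We will test the main effect of vitamin D supplementation (three groups) at 3 and 6 months". Under Missing Data it relies on the covariance structure of the repeated measurements, which is described only as random subject effects.

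**Sample size.** Section 9.2 expresses the target as a 25% relative improvement on a baseline FMD of about 6.5%, "assuming a standard deviation of 2.6% (conservative estimates based on published literature"). It does not say whether 2.6% is the SD of a single measurement or of a change.

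**The concern.** Sections 9.1 and 9.4 are a few paragraphs apart and name different primary outcomes, and section 9.5 lists both quantities as targets. If each arm has its own mean at every visit, the 6-month difference and the difference in change are separate contrasts. They differ by the chance baseline imbalance between arms and have different standard errors. If baseline means are held equal across arms, the two become one baseline-adjusted contrast. The text allows either model.

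Two things are at stake. The first is power: depending on the contrast and on what the 2.6% SD is, the trial may have clearly less than the planned 84%. The second is pre-specification: the 2.5% error rate per comparison holds only if a single contrast is fixed before the data are seen.

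**Working it through.** **Inputs.** From section 9.2: 56 completers per arm, difference 25% × 6.5 = 1.625 ≈ 1.6, SD 2.6, two-sided alpha 0.025, drop-out 25%. The documents give no correlation between visits. I assume r = 0.3, 0.5 and 0.7 between baseline and 6 months.

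**The plan's own figure.** Noncentrality is 1.6 / (2.6 × √(2/56)) = 1.6 / 0.491 = 3.26 on 110 df, giving power of 83.6% (84.8% with 1.625). Recruitment is 56 / 0.75 = 74.7, so 75 per arm and 225 in total. Both agree with the plan.

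**Two-sample power, 56 completers per arm.** With s the single-visit SD, the SD of change is s√(2(1−r)) and the baseline-adjusted SD is s√(1−r²). If 2.6 is the SD of change, then s = 2.6/√(2(1−r)) = 2.197, 2.600 and 3.357.

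| Reading of 2.6% | Contrast | r = 0.3 | r = 0.5 | r = 0.7 |
|---|---|---|---|---|
| SD of one visit | 6-month value | 84% | 84% | 84% |
| | change | 68% | 84% | 97% |
| | baseline-adjusted | 87% | 93% | 99% |
| SD of change | 6-month value | 94% | 84% | 60% |
| | change | 84% | 84% | 84% |
| | baseline-adjusted | 96% | 93% | 89% |

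**Power under the planned type of model.** This uses three visits, 75 per arm, equal correlations, and assumed monotone missingness of 12.5% at 3 months and 25% at 6 months. Generalised least squares gives the standard error (SE), and power is Φ(1.6/SE − 2.241).

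| Reading of 2.6% | Contrast | r = 0.3 | r = 0.5 | r = 0.7 |
|---|---|---|---|---|
| SD of one visit | 6-month value | 86% | 88% | 90% |
| | change | 74% | 88% | 98% |
| | common baseline | 88% | 94% | 99% |
| SD of change | 6-month value | 95% | 88% | 68% |
| | change | 88% | 88% | 87% |
| | common baseline | 97% | 94% | 91% |

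For the two low cells, 1.6/0.553 − 2.241 = 0.65 gives 74%, and 1.6/0.589 − 2.241 = 0.48 gives 68%. Simulating the common-baseline model with an estimated unstructured covariance (single-visit SD 2.6, 10,000 runs) gave 87%, 93% and 99%.

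**Leaving the contrast open.** Under the null, the 6-month value and the change have test statistics correlated √((1−r)/2) = 0.59, 0.50 and 0.39. The chance that at least one is significant at 0.025 for one dose pair is 4.5% to 4.8% (normal approximation, known variance). This is the exposure from not fixing the contrast, not a prediction of selective reporting.

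**Covariance, a separate and conditional point.** Suppose random subject effects means an intercept only, and the true correlations are 0.6 between adjacent visits and 0.36 from baseline to 6 months. The fitted common correlation is (0.6 + 0.6 + 0.36)/3 = 0.52. For change, the true variance exceeds the model's by (1 − 0.36)/(1 − 0.52) = 1.33. The effective critical value is 2.241/√1.33 = 1.94, so type I error is 5.2% against 2.5% nominal.

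| Correlations (adjacent; baseline to 6 months) | 6-month value | Common baseline | Change |
|---|---|---|---|
| 0.6; 0.36 | 2.5% | 4.3% | 5.2% |
| 0.6; 0.5 | 2.5% | 3.3% | 3.7% |
| 0.6; 0.6 | 2.5% | 2.5% | 2.5% |

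These are for complete data. With an unstructured covariance, the common-baseline model held 2.4% to 2.5% in all three settings (20,000 runs each, with the missingness above).

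**The case against.** Much is already fixed: dose pairs, time point, alpha and analysis population. A model listing time and treatment by time without a treatment main effect, with treatment tested only at 3 and 6 months, can be read as a common-baseline model. In that model change and 6-month value are the same parameter, and the three definitions agree. This is the best reading in the plan's favour. The text does not require it, because time is listed with baseline as a level, so an interaction over all three visits gives each arm its own baseline mean.

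It is also fair that the outcome definitions name only two quantities, and that the adjusted contrast enters only through the common-baseline reading. The completers-only lows of 68% and 60% are not for the planned model. Under that model the lows become 74% and 68%, which does not change the conclusion. The 68% cell requires a single-visit SD of 3.36, although the plan calls 2.6% conservative. Every correlation is assumed.

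The type I error point needs both an intercept-only model and decaying correlation, neither of which the plan states. It bears on the covariance, not on the outcome wording. Baseline adjustment is a preference among valid analyses. The inconsistency could be cured by naming any one contrast, but this choice protects power under both readings of the SD.

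**Conclusion.** The concern holds. The current text defines the primary outcome in two ways, and section 9.5 does not state the contrast. The expected treatment effect is the same under all readings, and the sample-size arithmetic is correct, so the consequence is for precision and pre-specification.

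Over assumed correlations of 0.3 to 0.7, an unadjusted contrast can fall well below the planned 84%. For change this happens if 2.6% is a single-visit SD and r is low. For the 6-month value it happens if 2.6% is the SD of change and r is high. The baseline-adjusted contrast stays above 84% throughout. Type I error inflation arises only under the two conditions named above. The plan should be amended, but the design is not invalid.

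**What to change.** In the synopsis and sections 9.1, 9.4 and 9.5, name one primary contrast: the baseline-adjusted difference in mean FMD% at 6 months, 1000 IU and 2000 IU each against 600 IU, alpha 0.025 per comparison. Estimate it with a repeated-measures model that holds baseline means equal across arms, or that uses baseline FMD as a covariate for the 3- and 6-month values, with an unstructured 3×3 covariance. If the common-baseline model was already intended, say so. In section 9.2, state whether 2.6% is the SD of a measurement or of a change. The missing-data sensitivity analyses in section 9.5 can stay as they are.

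The cost is wording in four places, one clause in section 9.2 and a few lines of code. No new data are needed, since FMD is measured at enrollment. The downside is six covariance parameters instead of the two of a random intercept, which is modest with about 225 children.

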### Missing Data

We do not expect substantial missing item-response data due to the electronic nature of data collection. Based on our pilot work, we anticipate <20% attrition at the 6-month assessment, and we have accounted for this in sample-size analyses. Participants who wish to discontinue the study drug will be asked to continue to participate in all follow-up visits; those who no longer wish to participate in the study will be considered dropouts, and we will monitor these events. We will obtain reasons for dropout in case it appears possible to modify the protocol so as to increase retention. At the end of the study, we will compare baseline characteristics and treatment arms between participants who have received 3- and 6-month assessments and participants who have not, to learn what factors are associated with missing visits.

For participants with missing 6-month outcome data, we will conduct several sensitivity analyses to test the impact on our study conclusions. The methods proposed assume that the data are missing at random (MAR), where the missing data mechanism is related to observed data, not the unobserved values. Although this assumption is difficult to confirm, our sensitivity analyses will allow us to assess the robustness of our findings and threats to the MAR assumption. Given that our outcomes are highly mechanistic and less patient-relevant symptomatic/functional outcomes, missing data at 6 months would likely be related to baseline characteristics or 3-month values. As mentioned previously, we will use linear mixed models for analysis, since these models are more robust to missing data than traditional multivariate models or single-point-in-time ANOVA. From these models, we can estimate the treatment impact at 6 months using the covariance structure of the repeated measurements. This approach will be compared to a complete case analysis (missing complete at random) and a nonignorable missing data method (pattern mixture modeling). These different methods should result in consistent qualitative results if our findings are robust to missing data.

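### The primary mixed model names only random subject effects; on its plain reading that assumes equal variance and equal correlation across visits, so the 6-month standard error can be wrong in either direction

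*Combined protocol and SAP*

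**What the plan says.** Section 9.5 (Data Analyses) fits FMD% at three visits with fixed effects for time and the treatment-by-time interaction "and random subject effects to test for differential changes in FMD over time and differences in FMD at six months". PWV uses the same method, and the metabolic outcomes use a model of the same form.

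The same section relies on the within-child dependence for missing data: "The mixed-effects model will allow unbiased estimation of the treatment effects at six months even if some 6-month data are missing", assuming missing at random. The Missing Data subsection adds that "we can estimate the treatment impact at 6 months using the covariance structure of the repeated measurements". Neither place says what that structure is. No random slope, visit-specific variance, residual correlation pattern, robust standard error or degrees-of-freedom method is given.

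The contrast is also left open. Section 9.5 states "We are primarily interested in the comparisons of each higher dose (1000 IU and 2000 IU) to the lower dose (600 IU) at six months", Section 9.4 states "Our primary outcome measure will be change in mean FMD% at 6-month follow-up", and Section 9.1 names FMD at the 6-month follow-up.

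**The concern.** A random intercept with independent residuals implies compound symmetry: the same SD at every visit, and a baseline-to-6-month correlation equal to that between adjacent visits. Repeated measures often depart from this, with correlation falling as the gap widens or spread changing during follow-up. The model then pools unequal variances and correlations into single values, and the reported standard error of a 6-month contrast can be too small or too large.

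Too small means that each of the two primary tests rejects too often at its nominal 0.025; too large means lost power. The planned sensitivity analyses (complete case, pattern mixture) vary the missing-data assumption and do not test the covariance. If the structure stays unnamed, it can also be chosen after the data are seen.

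**Working it through.** **Inputs from the documents.** 56 evaluable children per arm, difference 1.6, SD 2.6, two-sided alpha 0.025 (critical value z = 2.2414), accrual target 229 (Section 9.2); 1:1:1 allocation (Section 9.1).

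**Assumed.** 76 per arm (229/3). 26% missing at 6 months (56/76 = 0.74 observed), half of it already missing at 3 months, completely at random. All within-child correlations and visit-specific SDs are assumed, because the documents give one SD and no correlation.

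**1. The plan's own figure.** SE = 2.6 x sqrt(2/56) = 0.491. Power = Phi(1.6/0.491 - 2.2414) = 84.5% (83.6% by noncentral t). This reproduces "A sample size of 56 in each treatment group at the end of the trial would have 84% power". The calculation is a "two-sided two-sample comparison of means" and uses no correlation, so this point does not touch it.

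**2. Hand check with complete data.** Take 56 per arm, SD 2.6, correlations 0.6, 0.6 and 0.36. The random-intercept fit pools these to (0.6 + 0.6 + 0.36)/3 = 0.52, with variance 2.6^2 = 6.76.

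- Change from baseline, model SE: sqrt(2 x 2 x 6.76 x (1 - 0.52)/56) = 0.481.
- Change from baseline, true SE: sqrt(2 x 2 x 6.76 x (1 - 0.36)/56) = 0.556.
- Ratio 0.866. Actual error = 2 x [1 - Phi(2.2414 x 0.866)] = 0.052.
- Raw 6-month difference with separate means per arm and visit: model and true SE are both sqrt(2 x 6.76/56) = 0.491, so the error stays at 0.025.

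The choice of contrast therefore decides whether decay matters.

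**3. With missing data.** For 76 per arm and the dropout above, I found the compound-symmetry covariance to which the random-intercept model converges. I then compared its model-based SE with the true (sandwich) SE. Actual error = 2 x [1 - Phi(2.2414 x model SE / true SE)].

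SD 2.6, correlations 0.6 and 0.36:

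| 6-month contrast | Model SE | True SE | Actual error | Unstructured SE |
|---|---|---|---|---|
| Change from baseline | 0.459 | 0.527 | 0.051 | 0.523 |
| Common baseline mean | 0.413 | 0.458 | 0.043 | 0.448 |
| Raw difference, separate means | 0.469 | 0.477 | 0.0275 | 0.473 |

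**4. Other assumed covariances.**

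| Scenario | Change from baseline | Common baseline | Raw difference |
|---|---|---|---|
| SD 2.6, correlation 0.5 / 0.25 | 0.047 | 0.038 | 0.027 |
| SD 2.6, correlation 0.5 / 0.4 | 0.034 | 0.031 | 0.026 |
| SD rising 2.2, 2.6, 3.0 | 0.034 to 0.060 | 0.055 to 0.074 | 0.055 to 0.058 |
| SD falling 3.0, 2.6, 2.2 | about 0.02 to 0.045 | 0.008 to 0.020 | 0.007 to 0.008 |

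The ranges run over correlations from constant 0.5 to 0.6/0.36. Where the SE is too large, the loss is power: with falling SD and a common baseline, 96% against 99% with an unstructured covariance (constant 0.5), or 94% against 98% (0.6/0.36).

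**5. Unstructured covariance.** In large samples its SE is correct whatever the true covariance, so the error returns to 0.025. In every scenario its SE was no larger than the true SE of the random-intercept estimate.

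**The case against.** The strongest reply is that the plan never mentions a random intercept or compound symmetry. Its wording is plural, it does not exclude a random slope or a residual structure, and the Missing Data subsection refers to a covariance structure without naming one. That stands: a reader might infer that the plan forces compound symmetry, and it does not. But nothing else is specified, and a random intercept is what most analysts would fit from this text.

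A reader might also infer that the two primary tests do not hold 0.025. The documents cannot support that. For the raw 6-month difference with equal SDs, decay alone leaves the SE exactly right with complete data and nearly right with dropout. The larger figures need a change-from-baseline contrast, a common-baseline constraint that the plan does not state, or a change in SD. The SD path from 2.2 to 3.0 is a 36% rise (3.0/2.2 = 1.36) with nothing in the documents behind it. This makes the error conditional but does not remove it, because Section 9.4 defines the outcome as change, where decay matters most.

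A third tempting inference is that the missing-at-random argument collapses and the estimate is biased. A misspecified covariance can bias the estimate when missingness depends on observed values. However, the documents describe no arm-dependent dropout, their attrition projections differ (25% and 25-30% in Section 9.2, under 20% in Missing Data), and complete-case and pattern-mixture comparisons are planned. No bias of a given size is established.

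**Conclusion.** The concern holds in conditional form. The primary model is specified only by random subject effects. Read plainly, that assumes equal variance and correlation across visits, and no planned analysis checks or relaxes the assumption. With SD 2.6 and correlations 0.6/0.36, the per-comparison error is between 0.0275 and 0.051 depending on the contrast. Milder decay (0.5/0.4) gives 0.026 to 0.034, rising SD 0.034 to 0.074, and falling SD 0.007 to 0.045.

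These figures rest on assumed correlations, SD paths and missingness, and on large-sample approximations. They show what could happen, not what will. The change is worth making because it removes the dependence on an untested assumption at almost no cost.

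**What to change.** In Section 9.5, replace the random subject effect with an unstructured 3x3 within-child covariance, fitted by REML with a small-sample degrees-of-freedom method such as Kenward-Roger, for FMD%, PWV and the other repeated outcomes. State a fallback for non-convergence: a simpler structure with robust standard errors. Name this structure in the Missing Data subsection. Keeping the random intercept with a robust standard error would also address the SE problem, but not the reliance on the covariance when data are missing.

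State which 6-month contrast is primary (change from baseline, the difference under a common baseline mean, or the raw 6-month difference), and make Sections 9.1, 9.4 and 9.5 agree.

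Cost: six covariance parameters instead of two, which is negligible with about 225 children. No extra data or visits are needed. Make the change before unblinding.

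### Section 9.5 splits alpha as a fixed 0.025 for each dose; the split is valid, but Holm at an overall 0.05 would raise power for each dose and for both doses without more children

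*Combined protocol and SAP*

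**What the plan says.** **The two primary comparisons.** Section 9.5 is "primarily interested in the comparisons of each higher dose (1000 IU and 2000 IU) to the lower dose (600 IU) at six months" and gives each comparison a two-sided 0.025. It states no step-down rule.

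**Sample size.** Section 9.2 assumes a relative improvement "of at least 25% in children receiving each of the higher doses of vitamin D3 (1000 IU and 2000 IU") and none on 600 IU. It then states: "A sample size of 56 in each treatment group at the end of the trial would have 84% power", at two-sided 0.025, for a difference of about 1.6 points and an SD of 2.6. The revised accrual target of 229 rests on "power of at least 80% to detect the original effect size with 25%-30% attrition". No power is given for confirming both doses.

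**Success wording.** Section 9.4 says "A 25% or more improvement in FMD% in the 1000 IU or 2000 IU compared to the 600 IU group" will be considered significant. Sections 3 and 9.1 also use 'or'.

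**Outcome hierarchy.** The Design and Outcomes synopsis and Sections 9.1 and 9.4 make FMD% the primary outcome and list insulin sensitivity and the metabolic markers as secondary. The Objectives synopsis and Section 1.1(b) put those same markers in the primary objective. Section 9.5 uses both labels in one paragraph: "The second part of our primary analysis of our trial is to determine" the effect on these markers, and then the models will "test for differential changes in secondary outcomes over time". They are tested at 0.05, and for secondary outcomes Section 9.2 says "we have 89% power to detect effect sizes of 0.61 or greater without adjustment for multiplicity".

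**The concern.** A fixed split keeps 0.025 in reserve for the second dose even after the first has been declared significant. Holm releases it: the smaller p-value is tested at 0.025 and, if it is significant, the other at 0.05. Because Section 9.5 asks about each higher dose, the unused alpha costs power on a question the trial poses. The dose most affected is 1000 IU, since the plan's own 0/20/30% pattern gives it the smaller effect. The trial also has little slack: its target was cut from 252 because recruitment was slow, and it allows for 25 to 30% attrition.

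The labels matter less, but they do matter. If the metabolic markers can be called part of the primary analysis, a nominal result at unadjusted 0.05 could be presented as primary evidence.

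**Working it through.** **Inputs.** From Section 9.2: 56 completers per arm, SD 2.6, difference 1.6 points (25% of 6.5 = 1.625, rounded in the plan), and an alternative pattern of 0/20/30%, which is 0, 1.30 and 1.95 points. From Section 9.1: 1:1:1 allocation, so the two comparisons share the 600 IU arm and their test statistics have correlation 0.5.

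**Step 1: reproduce the plan's figure.** SE = 2.6 × √(2/56) = 0.491. Then 1.6/0.491 = 3.256, and 3.256 − 2.241 = 1.015, which gives a power of 84.5% (normal approximation). The two-sample t calculation gives 83.6%. The stated 84% holds.

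**Step 2: compare the two rules.**
- Fixed split: dose i is confirmed if p_i < 0.025.
- Holm: dose i is confirmed if p_i < 0.025, or if p_i < 0.05 and the other dose has p < 0.025.
- Hence power for both doses under Holm = power for both under the fixed split + the probability that one p-value is below 0.025 while the other lies between 0.025 and 0.05.

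At 56 per arm and 1.6 points in both doses, this is 74.2% + 8.3% = 82.5%. By symmetry each dose gains half of the 8.3%, so 84% becomes 88%.

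**Step 3: scenarios.** Simulated three-arm trials (at least one million per scenario), pooled variance, SD 2.6. Cells show fixed split → Holm.

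| Completers per arm | True effects (1000, 2000 IU) | 1000 IU | 2000 IU | Both doses | At least one |
|---|---|---|---|---|---|
| 56 | 1.6, 1.6 | 84% → 88% | 84% → 88% | 74% → 82.5% | about 94%, unchanged |
| 56 | 1.3, 1.95 | 65% → 74% | 95.5% → 96% | 64% → 74% | 96.5%, unchanged |
| 53 | 1.6, 1.6 | 82% → 86% | 82% → 86% | 71% → 80% | 92%, unchanged |
| 61 | 1.6, 1.6 | 87% → 91% | 87% → 91% | 79% → 86% | 95%, unchanged |

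The 53 is 229 × 0.70/3 = 53.4, the upper end of the attrition allowed in Section 9.2. The 61 is 229 × 0.80/3 = 61.1, for the attrition below 20% expected in the Missing Data section.

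The mixed model may also reduce the variance. The documents give no baseline to 6-month correlation, so this is an assumption. Using SD × √(1 − ρ²) at 56 per arm and 1.6 points, power for both doses goes from 79% to 87% if ρ = 0.3, and from 88% to 93% if ρ = 0.5.

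**Step 4: false claims.** With neither dose effective, any false claim occurs in 4.6% of trials under either rule. With one dose effective, the false-claim rate for the other is 2.5% under the fixed split. Under Holm it is about 4.4% (true effect 1.6) and reaches 5.0% when the effective dose is almost certain to be detected.

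**Step 5: what the extra rejections look like.** With the pooled t at 56 per arm, p between 0.025 and 0.05 corresponds to observed differences from 1.974 × 0.491 = 0.97 to 2.262 × 0.491 = 1.11 points. Allowing for variation in the sample SD, nearly all lie between 0.9 and 1.2 points. These are below the 1.6-point design effect. In each such trial a 97.5% interval for that dose includes zero. That is about 8% of trials with 1.6 points in both doses and 10% under 0/20/30%.

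**The case against.** **The fixed split is not wrong.** This stands. It controls the family-wise error, and the sample size was calculated on it. A reader might infer a type I error problem or an underpowered primary analysis; the documents support neither.

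**Success means 1000 IU or 2000 IU.** This also stands: for that question Holm adds nothing. A reader might take the 74% as a shortfall against a target of confirming both doses, but the plan sets no such target. In Section 9.2 the reference to each higher dose describes the assumed effect, and power is then given per comparison. On that per-comparison basis the gain is from 84% to 88%.

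**The extra rejections fall short of 25%.** Sections 9.1 and 9.4, read literally, call an improvement of 25% or more significant. If that applies to the observed difference, rejections at about 0.9 to 1.2 points add no successes. If 25% is the effect the trial was designed to detect, as in Section 9.2, the gain stands. The plan should say which.

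**Intervals and false claims.** Both costs are real. The 5% bound is unchanged, but Holm uses more of it when one dose works, and the simple match between test and 97.5% interval is lost.

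**The label.** One might infer that Section 9.5 merely contains a slip, or, conversely, that the metabolic markers are unadjusted co-primary outcomes. Neither follows. The wording tracks Section 1.1(b), so the conflict is not confined to Section 9.5. Yet every section that lists outcomes makes these markers secondary.

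**Conclusion.** This is a cheap improvement, not the correction of an error. Under the plan's own inputs (SD 2.6, 56 completers per arm, 1.6 points in both doses), Holm adds about 4 points of power per dose and about 8 points for confirming both. Under the 0/20/30% pattern it adds about 9 points for 1000 IU. It adds nothing to the chance of confirming at least one dose. The gains are somewhat smaller if attrition is below 20% or if the mixed model reduces the variance. They count only if 25% is a design effect and not a threshold on the observed difference. The disagreement over the metabolic markers is real but minor, and it needs the objectives, outcomes and analysis sections to be aligned together.

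**What to change.** 1. In Section 9.5, replace the 0.025 per comparison with: *The two 6-month FMD% contrasts with 600 IU will be tested by the Holm procedure at an overall two-sided alpha of 0.05: the smaller p-value at 0.025 and, if significant, the other at 0.05.* Limit this to these two contrasts. The p-values come from the mixed model already specified. The sample size in Section 9.2 is unchanged, and its 84% becomes a lower bound per dose under the same assumptions.
2. State that the Holm decision governs where a 97.5% interval includes zero, and acknowledge the higher false-claim rate when only one dose works.
3. State in Sections 9.1 and 9.4 that 25% is the design effect and not a threshold for the observed difference.
4. Reconcile the Objectives synopsis, Section 1.1 and Section 9.5 with the Design and Outcomes synopsis and Sections 9.1 and 9.4: 6-month FMD% is the sole primary outcome, and the metabolic-marker tests at unadjusted 0.05 are secondary.

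The cost is wording only, with no extra children, visits or data. The change should be made before the treatment code is broken.
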